3.2 Secondary Endpoint(s)

The secondary and exploratory endpoint(s) of this study are:

- socio-demographic characteristics: age, sex, occupation
- history of the disease and context of diagnosis: age at diagnosis, type of symptoms, exams that allowed the diagnosis and its confirmation, enzymatic assay value, genotype and presence or absence of family history
- medical history
- clinical evaluation criteria: weight (kg), height (cm), absence or presence (mild, moderate or severe) asthenia, abdominal pain, chronic bone pain, bone crises, syndrome bleeding, pulmonary impairment, neurological impairment
- clinical endpoints of liver and spleen:
 - Absence or presence of hepatomegaly, with the extent of the arrow (medio-clavicular line) (cm)
 - Absence or presence of splenomegaly, with the extent of the costal overhang (cm).-
- liver evaluation criteria and spleen MRI:
 - Absence or presence of hepatomegaly, with the extent of the arrow (medio-clavicular line) (cm)
 - Absence or presence of splenomegaly, with the extent of the costal overhang (cm)
 - Liver volume (m3)
 - Spleen volume (m3)
 - Presence or absence of myocardial, nodules, fibrosis, vesicular stones or other alterations.
- evaluation criteria of bone lesions by MRI (spine, pelvis, femurs, tibias and other symptomatic localization)

Absence or presence of bone lesions and their locations: bone infiltration, cortical thinning, osteonecrosis, bone infarction, stroke sequelae, vertebral compression fracture or other bone disease
- evaluation criteria of the biological parameters: hemoglobin (g/dl); leukocytes (cells/mm3); platelets (mm3); ACE (angiotensin converting enzyme (U/l); ferritin (mg/l); chitotriosidase (nmol/ h/ ml); CCL18 (ng/ml), vitamin D (nmol/L), vitamin B12 (pmol / l); SGOT / AST (U/l), SGPT / ALT (U/l), GGT (U/l), alkaline phosphatase (U/l), triglycerides (mmol/l), total cholesterol (mmol/l) gamma globulin (g/l) serum calcium (mmol/l) presence or absence of a monoclonal peak and the type if any

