8 PLANNED STATISTICAL METHODS

8.1 General Considerations

Statistical plan will be written and Statistical analysis will be conducted by CenBiotech using SAS 9.3 and under the authority of [name], Public health specialist and biostatistician, head of the medical evaluation Chair of the Business school of Dijon. A detailed analysis plan will be secondary provided and validated by Shire.

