8.2 Determination of Sample Size

There is no predefined sample size but in order to reflect daily practices, the study may include all patients presenting type 1 Gaucher disease and treated with VPRIV® in France.

So, based on data from the CETG, a sample size from 40 to 50 patients could be expected.

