8.5 Primary Endpoint(s) or Assessments

The changes pre and post treatment with velaglucerase alfa of the spine and femur BMB score will be described and compared using Wilcoxon signed-rank test. The analysis will be conducted successively on all MRI assessable and on optimal quality MRI only.

Primary Safety Endpoint(s)

Adverse events will be coded using MedDRA and described as recommended in ECH procedures as far as possible due in particular to retrospective conditions..

Primary Efficacy/Effectiveness Endpoint(s)

The values observed at the different follow up times and the variations between the reference MRI and the follow-up MRI, of the BMB weighted score at T1 and T2 measured at the femur and lumbar spine, are described by mean and standard deviation and the 95% confidence interval will be calculated. These values will be compared at the different follow up times with test on repeated data: ANOVA on repeated series or Wilcoxon rank test, depending on the nature and distributions of the studied variables.

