Changes over time of biological parameters (hemoglobinemia, leucocytes, platelets count, SGOT, SGPT, Gamma GT, alkalin phosphatases, converting enzyme angiotensin, ferritin, chitriosidase, gamma globulins, IgG, IgA, IgM, calcium level, D vitamin, B12 vitamin, triglycerides, cholesterol, monoclonal peak) will be analysed using variance analysis on repeated series.

Logistic regression type shall be used to determine criteria influencing positive or negative evolutions. The analysis on MRI parameters will be conducted successively on all MRI assessable and on optimal quality MRI only.

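### Section 8.6 relates patient factors to change only through a positive/negative logistic model, which loses power for graded or continuous parameters in 40 to 50 patients

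*Protocol*

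**What the plan says.** After listing the within-patient tests for each group of secondary criteria, Protocol section 8.6 adds: "Logistic regression type shall be used to determine criteria influencing positive or negative evolutions". It does not say which parameter's evolution is meant, where positive ends and negative begins, or which criteria are candidates. The next sentence applies to MRI parameters generally: "The analysis on MRI parameters will be conducted successively on all MRI assessable and on optimal quality MRI only".

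On size, section 8.2 says "There is no predefined sample size but in order to reflect daily practices" and then that "a sample size from 40 to 50 patients could be expected".

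The other methods in sections 8.5 and 8.6 (signed-rank and other rank tests, McNemar tests, repeated-measures ANOVA) are named for change over time within patients. None is assigned to relating patient characteristics to that change, although section 2.2 wants, if possible, treatment-naive and previously treated patients compared on the evolution of MRI parameters.

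Section 8.1 defers detail: "A detailed analysis plan will be secondary provided and validated by Shire".

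**The concern.** The model class, the two-way outcome and the aim of determining influences are fixed in the protocol, so an analysis plan that follows the protocol inherits them.

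Many of the parameters do not come in two classes. BMB items are graded codes (sections 6.6 and 6.7), and organ volumes and laboratory values are continuous. A patient whose value does not change is neither positive nor negative, so a binary model must put that patient in one class or leave the patient out. A small and a large improvement count the same. In a cohort of 40 to 50 this loss of information is costly, and the smaller class may be too small for more than one or two predictors.

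At stake is the quality of the answer to which patients improve. Section 4.1 says that results go to regulatory agencies, and section 1.3 that they partly answer a request from the French Transparency Commission. Real determinants could be missed, and a model with too many criteria could report spurious ones.

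**Working it through.** **No figure to reproduce.** The protocol gives no power, significance level or effect size for this analysis; 40 to 50 is a feasibility expectation.

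**Inputs.** From the documents: 40 to 50 patients (section 8.2) and a positive/negative outcome (section 8.6). Assumed: two-sided 5% test; one normally distributed factor with correlation 0.3 or 0.4 to the change; 20% to 50% of patients in the smaller class, 40% improved in the central case.

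**1. Size of the smaller class.** Patients × share:
- lowest: 40 × 0.20 = 8
- highest: 50 × 0.50 = 25

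By the convention of ten events per predictor, 8/10 = 0.8 and 25/10 = 2.5, so about one or two predictors. The repeat on optimal-quality MRI can only lower this.

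**2. Power lost by splitting a continuous change.** Simulated, 2,000 runs per setting; linear analysis of the change against a logistic model (likelihood-ratio test) with 30% or 50% improved:

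| n | correlation | change itself | split, logistic |
|---|---|---|---|
| 40 | 0.3 | 48–49% | 31–35% |
| 40 | 0.4 | 74–75% | 50–54% |
| 50 | 0.3 | 57–59% | 38–40% |
| 50 | 0.4 | 84–85% | 61–66% |

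The loss is about 14 to 26 percentage points.

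**3. Central case, and a coarser outcome.** n = 45, correlation 0.4, 40% improved:
- continuous change: about 80% against 56%, a loss of 24 points
- three classes (assumed 10% worse, 50% same, 40% better): about 66% against 54%, a loss of 12 points

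A recheck with 4,000 runs gave 80% (continuous, linear), 68% (three classes, linear) and, for the binary logistic model, 55% with a Wald test and 61% with a likelihood-ratio test. The test therefore matters: with the likelihood-ratio test the losses are 80 − 61 = 19 and 68 − 61 = 7 points.

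**4. Does the replacement recover power?** Proportional-odds against binary logistic on the same three classes (1,500 runs, of which 1,493 contained all three classes): 65% against 53% with Wald tests, 68% against 59% with likelihood-ratio tests. The gain is 9 to 12 points. These runs have one factor and no adjustment for the reference value.

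**5. Room for two or three factors.** With the reference value they make three or four coefficients. In a linear model that is 40/4 = 10 to 50/3 ≈ 17 patients per coefficient.

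**The case against.** The strongest reply is that outcome definitions, covariate lists and selection rules belong in the analysis plan, which section 8.1 promises. That stands, and no point is made of their absence. What remains is the choice the protocol does make: a logistic model on a positive/negative outcome.

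Two further replies stand in part. The word evolutions is used for all secondary criteria, and several of these are binary (nodules, infarcts, osteonecrosis); logistic regression is an ordinary choice there. The phrase logistic regression type may also admit an ordinal model, although positive or negative points to two classes.

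The objectives are descriptive, section 3.2 calls the endpoints secondary and exploratory, and the sample size does not rest on this regression. That limits the weight of the point but does not make the split a good method.

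Three stronger readings are tempting, and the documents do not support them:
- *That more than 20 criteria will be searched.* The sentence before the logistic one names 20 laboratory parameters ("Changes over time of biological parameters (hemoglobinemia, leucocytes, platelets count, SGOT, SGPT, Gamma GT, alkalin phosphatases, converting enzyme angiotensin, ferritin, chitriosidase, gamma globulins" and others), but as outcomes for repeated-measures ANOVA. Nothing ties them to the logistic model. Screening 20 independent null criteria at 5% would give 1 − 0.95^20 = 64% for at least one false finding; at an assumed pairwise correlation of 0.3 or 0.5 this drops to 55% or 42%. These figures illustrate the unguarded risk and do not describe a planned analysis.
- *That the study throws away the score change.* Section 8.5 keeps it: "The changes pre and post treatment with velaglucerase alfa of the spine and femur BMB score will be described and compared using Wilcoxon signed-rank test".
- *That the baseline BMB score is left out although it is the main determinant.* The protocol neither includes nor excludes any covariate, and nowhere ranks determinants.

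**Conclusion.** The point holds for ordinal and continuous parameters. In the central case (45 patients, correlation 0.4, 40% improved), splitting the change costs about 24 percentage points of power if the change is continuous and about 12 if it has three classes; with a likelihood-ratio test these become about 19 and 7. The figures rest on a normal underlying change, one normally distributed factor and an assumed share improved, none of which the documents give. The direction was the same in every setting tried.

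At an assumed share of 20% to 50%, the smaller class of 8 to 25 patients carries about one or two predictors, so claiming to determine influencing criteria promises more than the data can give. Overfitting is a risk that the protocol does not guard against, not something that it plans. For binary criteria the method is suitable. The primary BMB change analysis is not affected, so this is a moderate point about one secondary analysis.

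**What to change.** Reword the logistic sentence in section 8.6 and carry it into the analysis plan:

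- For ordinal or continuous parameters, model the follow-up value with a proportional-odds or linear model, adjusted for the value at the reference MRI.
- Fix two or three factors beforehand, for example treatment-naive versus previously treated (which would also serve the comparison in section 2.2) and time on VPRIV. Use the lower number where the scale is coarse or the optimal-quality set is small.
- Keep logistic regression for criteria that are truly binary, with about one or two predictors.
- Report estimates with 95% confidence intervals, and replace the verb determine by explore.

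The same data are used and only wording changes. The price is that fewer factors are examined, and the proportional-odds assumption can be checked only roughly in a sample of this size.

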8.7 Interim Analysis

All data analysis previously described will be conducted at the end of the study scheduled on February 2018.

9 ADMINISTRATIVE CONSIDERATIONS

9.1 Investigators and Study Administrative Structure

All the financial convention between Shire and the medical practitioners will be submitted for approval to the National Board of Medical Professional and declare to the French administrative authorities according the reference procedure.

The Investigator should ensure that all persons assisting with the study are adequately informed about the protocol, any amendments to the protocol, the study treatments, and their study related duties and functions. The Investigator must maintain a list of sub-investigators and other appropriately qualified persons to whom he or she has delegated significant study related duties.

9.2 Institutional Review Board or Independent Ethics Committee Approval and Other Governing Regulatory Bodies

The protocol, the CRF and the informed consent of this observational study have be approved by the CCTIRS.

9.3 Study Monitoring

Good Pharmacoepidemiological (GPPs) guidelines for observational studies will be followed. Review of the eCRF's for completeness and clarity, cross-checking with source documents, and clarification of administrative matters will be performed.

The study will be monitored by the Sponsor or its designee. Monitoring will be performed by a representative of the Sponsor (Clinical Study Monitor) who will review the eCRFs and source documents. The site monitor will ensure that the investigation is conducted according to protocol design and regulatory requirements by frequent site visits and communications (letter, telephone, and facsimile) and in accordance with current GPPs and the respective local and French government regulations and guidelines. Records and data may additionally be reviewed by auditors or by regulatory authorities.

The Sponsor ensures that Local Regulatory Authority requirements are met before the start of the study. The Sponsor (or a nominated designee) is responsible for the preparation, submission, and confirmation of receipt of any Regulatory Authority approvals required.

9.4 Case Report Forms and Study Records

The clinical data are extracted from the medical record of the patients and are reported on the paper form. Forms are then transmitted by mail to the CRO which records it (double entry) on a computerized CRF developed on capture system. Automatic control of data entry and automatic request on missing data or data not fulfilling the control quality previously described in accordance with the laboratory are issued and transmitted to the medical practitioner

Case report forms (paper) are provided for each patient. All forms must be filled out by authorized study personnel. All corrections to the original CRF entry must indicate the reason for change. The Investigator is required to sign the CRF after all data have been captured for each patient. If

corrections are made after review and signature by the Investigator, he or she must be made aware of the changes, and his or her awareness documented by resigning the CRF.

9.5 Critical Documents

Before Shire Rare diseases initiates the study (ie, obtains written informed consent from the first patient), it is the responsibility of the Investigator to ensure that all required documents are available to Shire Rare diseases or their designee. Examples include:

- Curricula vitae of Investigator and sub-investigator(s) (current, dated and signed within 12 months of study initiation)
- Signed and dated agreement of the final protocol
- Signed and dated agreement of any amendment(s), if applicable
- Approval/favorable opinion from the CCTIRS and by the National Board of Medical Practitioner clearly identifying the documents reviewed by name, number and date of approval or re approval: protocol, any amendments, Subject Information/Informed Consent Form, and any other written information to be provided regarding subjects recruitment procedures
- Copy of CCTIRS approved Subject Information/Written Informed Consent Form/any other written information

Regulatory approval and notification as required must also be available; these are the responsibility of Shire Rare diseases.

9.7 Protocol Violations/Deviations

The Investigator will conduct the study in compliance with the protocol. The protocol will not be initiated until the CCTIRS and the appropriate regulatory authorities have given approval/favorable opinion. Modifications to the protocol will not be made without agreement of the Sponsor. Changes to the protocol will require written IRB/IEC approval/favorable opinion prior to implementation, except when the modification is needed to eliminate an immediate hazard(s) to patients.

The CCTIRS may provide, if applicable regulatory authorities permit, expedited review and approval/favorable opinion for minor change(s) in ongoing studies that have the approval/favorable opinion of the CCTIRS. The Sponsor will submit all protocol modifications to the regulatory authorities in accordance with the governing regulations.

When immediate deviation from the protocol is required to eliminate an immediate hazard(s) to patients, the Investigator will contact the Sponsor or its designee, if circumstances permit, to discuss the planned course of action. Any departures from the protocol must be fully documented as a protocol deviation.

Protocol deviations will need to be reviewed by the medical monitor and may also be required to be submitted to the CCTIRS.

Protocol modifications will only be initiated by the Sponsor and must be approved by the CCTIRS or other applicable international regulatory authority before initiation.

9.8 Premature Closure of the Study

If the Sponsor, Investigator, or regulatory authorities discover conditions arising during the study which indicate that the clinical investigation should be halted due to an unacceptable patient risk, the study may be terminated after appropriate consultation between the Sponsor and the Investigator(s). In addition, a decision on the part of the Sponsor to suspend or discontinue development of the product may be made at any time. Conditions that may warrant termination of the study or site include, but are not limited to:

- The discovery of an unexpected, significant, or unacceptable risk to the patients enrolled in the study
- Failure of the Investigator to comply with pertinent global regulations
- Submission of knowingly false information from the study site to the Sponsor or other pertinent regulatory authorities
- Insufficient adherence by the Investigator to protocol requirements

9.9 Access to Source Documentation

Regulatory authorities, the IRB/IEC, or the Sponsor may request access to all source documents, CRFs, and other study documentation for onsite audit or inspection. Direct access to these documents must be guaranteed by the Investigator, who must provide support at all times for these activities. Monitoring and auditing procedures that comply with current GCP or GPP (where relevant) guidelines will be followed. On-site review of the CRFs for completeness and clarity, crosschecking with source documents, and clarification of administrative matters may be performed.

9.10 Data Generation and Analysis

The clinical database will be developed and maintained by Cenbiotech (a contract research organization) or an electronic data capture technology provider as designated by Shire Rare diseases. Cenbiotech will be responsible for performing study data management activities. Data will be recorded using double entry

Adverse events will be coded using Medical Dictionary for Regulatory Activities (MedDRA). Concomitant medication will be coded using WHO-Drug Dictionary (WHO-DD). Centralized laboratories will be employed as described in the study manual to aid in consistent measurement of efficacy and safety parameters.

9.11 Retention of Data

Essential documents should be retained until at least 2 years after the last approval of a marketing application and until there are no pending or contemplated marketing applications or at least 2 years have elapsed since the formal discontinuation of clinical development of the investigational product. The Sponsor will notify the Investigator if these documents must be retained for a longer period of time. It is the responsibility of the Sponsor to inform the Investigator or institution as to when these documents no longer need to be retained.

Appendix 2 Overview of the Study Design

	0. Eligible patients (n= 40-50)	
	1. Patient inclusion (Written informed consent obtained)	
Retrospective data collection	
2. Retrospective data collection
 
The closest MRI conducted during the 5 years before the initiation of VPRI[®] treatment or in the 3 months after the VPRI[®] initiation is collected and defined as the reference MRI.
 
Clinical and biological data available 3 months before or after the reference MRI are collected
 
Medical history and clinical and biological data available, when VPRI[®] treatment is initiated, are collected
 
Each MRI available since VPRI[®] treatment initiation and patients inclusion is collected as well as clinical and biological data available 3 months before or after it
 
.....
 
MRI collected are anonymously sent to a central lab reading: MRI results data collection
	
Medical history
 
Clinical data
 
Laboratory data
 
VPRI[®] treatment
 
MRI
 
..... VPRI[®] treatment
 
Centralized MRI reading:
 
 - Liver and spleen volumes - BMB score of the spine and femur
Prospective data collection	
3. Prospective follow-up:
 
For each MRI that will be conducted from the patient inclusion until the end of the one year follow up study, clinical and laboratory data available within the 3 months before the MRI and the 3 months after MRI are collected.
 
.....
 
.....
 
MRI collected are anonymously sent to a central lab reading: MRI results data collection
	
Clinical data
 
Laboratory data
 
VPRI[®] treatment
 
MRI
 
.....
 
Centralized MRI reading:
 
 - Liver and spleen volumes - BMB score of the spine and femur

Appendix 3

Protocol Signature Page

Study Title:

Retrospective and prospective observational study of patients
with type 1 Gaucher disease treated with VPRIV® (velaglucerase
alfa)

Study Number: RMGF - SHPGCB-703

Final Date: 05/04/2016

Amendment Date:

Sponsor's Approval

This study has been approved by Shire Rare diseases.

Signatory:

Sponsor

25/04/2016

Signature

Date

[name]

Printed Name

Investigator's Acknowledgement

I have read the protocol described above. I agree to comply with all applicable regulations and to conduct the study as described in the protocol.

Signatory:

Investigator

Name Title

Institution

